Stressor-evoked brain and cardiovascular responses to stress.

NCT05413512

Date: 02/20/2020

Study Description

Title	Stressor-evoked brain and cardiovascular responses to acute psychological stress
Principal Investigator	[name].
Study location(s)	Baylor University, Waco, Texas
Objectives	The main objective of Study 1 is to examine the relationship between cardiovascular, metabolic, and neural responses to acute psychological stress in healthy adults.
Main Inclusion/Exclusion Criteria	Participants may participate if they are between the ages of 18-30 and will be recruited from the surrounding area. Exclusion criteria will include: 1) any history of chronic medical or neurological disorder (e.g., traumatic brain injury, cardiovascular disease), 2) metal exposure, aneurysm clips, pacemaker, claustrophobia, cochlear implant or colorblindness, 3) current illness or infection, and 4) any condition that would prohibit them from engaging in a physical exercise testing session.

TABLE OF CONTENTS

[figure not shown]
1.0 Background and Rationale	4
2.0 Study Objectives	5
3.0 Subject Selection and Recruitment	5
3.1 Inclusion Criteria	5
3.2 Exclusion Criteria	5
3.3 Recruitment	5
3.4 Consent	5
4.0 Research Design & Methods and Study Visits	6
5.0 Risks and Benefits	9
6.0 Statistical Analysis	10
7.0 Data Security & Privacy/Confidentiality	11
8.0 Data & Safety Monitoring	11
9.0 Study Location	11
10.0 Dissemination Plan	11
11.0 References	12

1.0 BACKGROUND AND RATIONALE

Significance: Cardiovascular disease (CVD) and cardiovascular outcomes are a leading burden to public health¹ and the risk levels of CVD from psychological stress are comparable to the level of risk conferred by smoking and physical inactivity². A stressor-evoked cardiovascular reaction to psychological stress (i.e., rapid and autonomically mediated rises in blood pressure and heart rate) may be adaptive. However, some individuals have an exaggerated stress response, and we have shown that exaggerated cardiovascular reactions to stress predict CVD mortality³. Over the long-term, such exaggerated stressor-evoked cardiovascular reactions may initiate or exacerbate pathophysiological changes on the heart and vasculature⁴. Unfortunately, the current state of knowledge is strictly correlational. We lack an understanding of the neural basis for the generation of exaggerated cardiovascular reactions that are excessive to the immediate physiological needs of the individual. We expect to identify the initial neural correlates of how psychological stress-related processes instantiated in the brain relate to metabolically exaggerated cardiovascular stress responses, providing important groundwork for identifying how these processes may be intervened upon to reduce associated CVD risk.

Scientific Premise: The overall premise of the proposed work is based upon over three decades of research and meta-analyses suggesting that individual differences in cardiovascular responses to acute psychological stress are associated with future disease outcomes. Two key areas provide a basis for this project:

Autonomic responses to stress and future cardiovascular disease risk. There is longstanding and cumulative epidemiological evidence that individuals who exhibit a phenotype characterized by the expression of large-magnitude cardiovascular reactions are at elevated risk for clinical and preclinical endpoints of CVD⁵⁻⁸. My work and the work of others demonstrates that individual differences in these responses are relatively stable⁹⁻¹³. Moreover, cardiovascular responses during acute psychological stress, stress that does not require physical exertion, can be metabolically inappropriate—meaning that the cardiovascular system is working in excess of metabolic demand¹⁴⁻²⁴. To determine if cardiovascular responses are metabolically appropriate, we measure oxygen consumption (marker for metabolic activity) and cardiovascular activity at rest and during a graded exercise test. The cardiovascular and metabolic responses to moderate exercise is a marker for metabolically appropriate heart rate changes¹⁴. Individual regressions of oxygen consumption on heart rate are calculated based on measurements during exercise. The computed regressions for each participant are then used with their oxygen consumption scores recorded during stress to “predict” what their heart rate should be during baseline and acute psychological stress. The difference between observed heart rate and predicted heart rate is called additional heart rate, which represents heart rate in excess of metabolic demand (i.e., the degree to which the heart is responding inappropriately or in excess during psychological stress). Figure 2 displays a representation of predicted heart rate versus actual heart rate during a standard psychological stress testing paradigm¹⁴. The lack of physical exertion during psychological stress does not perturb the metabolic system, which results in predicted heart rate being the same as rest. However, participants, on average, demonstrate an increase in heart rate in excess of the metabolic demand. A longstanding view is that the repeated and cumulative expression of such metabolically-disproportionate, stressor-evoked, cardiovascular reactions contribute to, or exacerbate, pathophysiological changes that are conducive to CVD and CVD events among vulnerable individuals¹⁴⁻¹⁷. Recently, it has been proposed that the brain generates anticipatory visceromotor commands to alter cardiovascular physiology to prepare individuals to cope with psychological stressors²⁵ and that these commands are “visceral predictions”, insofar as to anticipate behavioral demands engendered by appraised stressors^{26,27}. Individuals with metabolically disproportionate responses may be displaying visceral prediction errors²⁸. The proposed work is both conceptual and empirical and provides a rationale for examining, in the context of CVD risk, the relationship between brain systems for visceral control and body metabolically exaggerated responses to stress.

Brain-imaging studies of stressor-evoked cardiovascular reactivity. Recent meta-analyses have identified core components of a broad network of forebrain systems involved stressor-evoked changes in cardiovascular activity^{25,30-33}. These forebrain areas functionally interact with one another to modulate visceromotor and viscerosensory functions of cell groups within areas that govern and monitor autonomic and neuroendocrine outflow to the heart and blood vessels in coordination with behavioral actions and motivated dispositions to act³⁴⁻³⁶. Recent studies address previous limitations in stressor-evoked neuroimaging research by examining how patterns of responses, rather than voxel-by-voxel analyses, predict the likelihood of a certain magnitude of cardiovascular response^{37,38}. Using multivariate and cross-validation methods allows for more rigorous statistical testing and more generalizable results that could identify a brain phenotype that reflects CVD risk^{38,39}. Although it is the metabolically-disproportionate, stressor-evoked, cardiovascular reactions that are thought to most closely link with pathophysiological changes in vulnerable individuals, previous work in the field has only examined the neural correlates of stressor-evoked cardiovascular changes (i.e., cardiovascular reactivity)^{9,25,37,40-42}. This study will be the first study to directly test the hypothesis that metabolically-disproportionate, stressor-evoked, cardiovascular reactions are associated with ‘visceral prediction’ errors²⁸.

2.0 STUDY OBJECTIVES

The main objectives of this study are to examine cardiovascular, metabolic, and neural responses to acute psychological stress. Additionally, the long-term goal of the study is to identify the multivariate pattern of stressor-evoked brain activity that reliably predicts individual differences in metabolically excessive responses to acute psychological stress.

3.0 SUBJECT SELECTION & RECRUITMENT

3.1 INCLUSION CRITERIA

One hundred and fourty participants (at least 50% female) between the ages of 18-30 years will be recruited from the surrounding area.

The age range was selected based on a recent meta-analysis by my colleagues and I, which demonstrated that participants ages 18-30 have different cardiovascular reactivity compared to those over 30⁴³. The sample will be representative of the greater Waco demographics.

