Visit 1 Measurements: Cardiovascular activity will be measured continuously⁴³ throughout the protocol using electrocardiogram and will be calculated for each minute of the protocol using Mindware Kubios processing software³⁴. Body metabolic rate, indexed by oxygen consumption, will be measured on a breath-by-breath basis assessing ventilation and analyzing inspired and expired gas composition using an integrated system. Metabolic rate will then be averaged for each minute. Additional heart rate will be calculated by first computing individual regressions of oxygen consumption on heart rate using data from rest and each of the 4-minute bouts of the graded exercise test¹⁴. The computed regressions for each participant will then be used, with each individual's observed oxygen consumption recorded during stress, to "predict" what heart rate should be during baseline and during the MSIT (acute psychological stress). The difference between observed heart rate and predicted heart rate will be additional heart rate, which represents heart rate in excess of body metabolic demand.

Visit 2 Protocol: Visit 2 is designed to measure stressor-evoked neural activity, required to develop multivariate analyses to predict metabolically excessive responses (i.e., additional heart rate). The same 150 participants will come to the VINS 17 CoE to engage in a functional magnetic resonance imaging protocol. The protocol will consist of a structural scan, followed by a functional scan during which participants will engage in the MSIT and Stroop.

Visit 2 Measurements: Functional and structural images will be obtained on a Philips Ingenia 3.0 Tesla Omega MRI scanner equipped with a 32-channel head coil. Blood-oxygen level-dependent (BOLD) images will be acquired over the stressor

[figure not shown]
period with the following parameters: FOV = 205 x 205 mm², matrix size = 64 x 64 mm², TR = 2,000 ms, TE = 28 ms, and FA = 90°. Functional scans will be obtained at rest and during an acute psychological stress task (MSIT).

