5.0 RISKS & BENEFITS

Study 1 Risks

- Exercise Task:
 - Some participants may find it difficult to complete the exercise portion of the task. Individuals who have been advised not to exercise by a doctor are excluded from participating in the study. Participants will be told they can stop at any time if they are feeling ill from exercise. Additionally, participant’s perceived exertion will be measured to ensure they are not at their maximum exertion for too long. In extreme cases, participants may experience cardiac problems associated with exercise. There is a defibrillator in the building where exercise testing will occur. Participants who meet eligibility criteria will be required to perform a sub-maximal exercise test. The participants will likely experience muscle soreness in their legs for between 24 to 48 h after exercise. This soreness is completely normal, and as these individuals will be inexperienced exercisers, they will receive ample warning regarding the risk.
 - Muscle strains or pulls resulting from the exercise testing sessions are also possible. However, prior to and during each exercise session, the participants will be familiarized with the exercise protocol and the correct technique required to perform the exercise safely on the treadmill. Therefore, we aim to minimize potential injury through proper instruction and protocol familiarization.
 - Trained, non-physician exercise physiologists certified in CPR will supervise participants undergoing testing and assessments. An automated electronic defibrillator (AED) is located in the Baylor Science Building and no less than two researchers will work with each participant during testing sessions. In the event of an emergency, one researcher will check for vital signs and begin intervention if required, while the other researcher contacts Baylor’s campus police at [name]. All emergency procedures are posted above the phones in the event any other research investigator(s) is at hand to provide assistance.
- Stress Task:
 - The risks associated with the acute psychological stress task are minimal. The paradigm being used has been tested on thousands of people and no adverse side effects, other than feeling stressed during the task, have been experienced.
- functional Magnetic Resonance Imaging (fMRI):
 - There are some inherent risks associated with MRI in regard to metal implants. Entering the scanner with metal can cause risk to the machine and the participants.

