 - We will ensure that all participants undergo a thorough screen to determine eligibility for the fMRI. Participants who have metal within them such as: aneurysm clips or pacemakers, will be excluded. There are known dangers from MRI to people with heart pacemakers, with the possibility that the pacemaker may malfunction, as well to people with metal implanted devices such as aneurysm clips that might be moved in a dangerous manner.
 - Participants will be asked questions about metal exposure throughout their lifetime and will be screened

- with a metal detector to make sure they have not left any metal on their person.
- There are no known effects of the magnetism or radio waves used in MRI.
- Some people may become claustrophobic while in the machine. Should this occur, the examination will end and they will be quickly removed from the scanner. This is an occasional negative event that is usually mild in severity and quickly resolved upon leaving the scanner.
- Electrocardiography
 - Electrocardiography (ECG) carries minimal risk. However, some individuals may have skin irritation or an allergic reaction from the electrodes (sticky pads) being used. If you find the sticky pads are causing too much irritation, please let the researcher know and they can be removed.
- Loss of Confidentiality
 - A risk of taking part in this study is the possibility of a loss of confidentiality. Loss of confidentiality includes having your personal information shared with someone who is not on the study team and was not supposed to see or know about your information. The researcher plans to protect the participants' confidentiality through standard procedures noted in this form.

Incidental Findings:

- While the testing procedures the participants will undergo during this study are for research purposes only, there is the possibility the researchers may note a result potentially important to the participant's health. In this event, the participant in question will be contacted to explain the observation. If they do not have a private physician, we will refer them to an appropriate clinic for follow-up. Proceeding with any additional tests and/or treatments, if required, will be left to their discretion, and the participant or their insurance company will be responsible for any costs incurred.

Benefits:

- Possible benefits include participants learning a little bit more about themselves and how they cope with stress.

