6.0 STATISTICAL ANALYSIS

All participants will receive a unique ID for the study. IDs will be given starting with the number 9000. Questionnaire data will be collected through the Qualtrics survey system using tablets in the laboratory. Qualtrics will store the data on an encrypted server that will only be accessed by the Co-Investigator, primary RA, and students working on the study.

Analytic plan: Averages of the main study variables will be calculated for the main analyses of examining cardiovascular, metabolic, and neural activity at rest and during the acute psychological stress task. Reactivity will be calculated as: Stress activity – Baseline activity. fMRI data will be preprocessed and analyzed with statistical parametric mapping software (SPM12; <http://www.fil.ion.ucl.ac.uk/spm>) using established realignment, co-registration, smoothing, and motion correction analyses³⁸. Stressor-evoked brain activation will be determined by comparing the BOLD signal activity during the incongruent (stress) versus congruent (control) condition^{9,38}. For the analyses between stressor-evoked cardiovascular activity and stressor-evoked neural activity, machine learning techniques will be used to generate a multivariate pattern (3D regression weight map) that relates to heart rate and metabolic responses to stress. The study will then test if this generated multivariate pattern can reliably predict cardiovascular and metabolic responses to stress. Recent papers examining brain multivariate pattern prediction of cardiovascular responses to stress found the between subjects correlations to be relatively small, $r = \sim .20$. Based on these results, with alpha set at .05 and power = .80, it is estimated we will need a sample of at least $N = 140$.

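### The recruitment target equals the stated minimum of 140, so the plan has no margin for participants without usable data from both visits, and a conflicting figure of 150 is left unexplained

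*Combined protocol and SAP*

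**What the plan says.** Section 3.1 sets recruitment: "One hundred and fourty participants (at least 50% female) between the ages of 18-30 years will be recruited". Section 6.0, working from a between-subjects correlation of about .20 and "with alpha set at .05 and power = .80", concludes that "it is estimated we will need a sample of at least" 140. It does not say whether the test is one- or two-sided.

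Section 4.0 gives a different number for the imaging visit: "The same 150 participants will come to the VINS 17 CoE to engage in a functional magnetic resonance imaging protocol".

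The analysis that the sample size supports draws on both visits. Under Section 4.0, additional heart rate comes from Visit 1 (rest, stress and the four 4-minute cycling bouts), and stressor-evoked neural activity comes from Visit 2.

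The plan itself names three ways to lose a participant from that analysis:

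- Section 3.4 allows withdrawal at any time.
- Section 5.0 says of the exercise test: "Some participants may find it difficult to complete the exercise portion of the task", and lets participants stop if they feel ill.
- Section 5.0 says of the scan: "Some people may become claustrophobic while in the machine. Should this occur, the examination will end".

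The document gives no expected loss rate, no inflation of the target, no replacement rule and no rule for missing data.

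**The concern.** The number recruited and the minimum number needed are the same. Once one participant lacks usable data from either visit, the analysable sample is below the plan's own minimum. With two visits, an exercise test and an MRI scan, some loss is foreseeable from the plan's own text.

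The figure of 150 does not resolve this. If 140 are recruited, the same 150 cannot return. If 150 are enrolled, Section 3.1 is wrong, and nothing says that the extra 10 are there to cover losses.

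At stake is the power statement. A reader of Section 6.0 will take 80% as the power of the planned analysis, but the plan does not show that 140 people will be in that analysis. This gap is separate from how 140 was derived and would remain if the derivation were corrected.

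**Working it through.** **Inputs.** Recruitment target 140 (Section 3.1). Required number at least 140, alpha .05, power .80, r about .20 (Section 6.0). Visit 2 number 150 (Section 4.0). Sidedness is not stated, so both are shown. Loss rates are not stated, so 5% to 20% is assumed as a range.

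**Formulas (Fisher z, one correlation).**

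- N = ((z_alpha + z_beta) / atanh(r))^2 + 3
- Power = Phi(atanh(r) × sqrt(N − 3) − z_alpha)
- z_alpha = 1.960 two-sided or 1.645 one-sided; z_beta = 0.842; atanh(.20) = 0.2027

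**Step 1: the plan's own figure.** At r = .20:

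- Two-sided: (2.802 / 0.2027)^2 + 3, which rounds up to 194.
- One-sided: (2.486 / 0.2027)^2 + 3, which rounds up to 154.

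An exact bivariate-normal calculation gives 193 and 153. The stated 140 is not reproduced. It gives 80% power only at r = .235 two-sided or about .21 one-sided.

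**Step 2: power after losses from 140.** The first power column takes the plan's 80% at 140 at face value (r = .235, two-sided). The other two use the plan's r of .20.

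| Lost (assumed) | Analysed | r = .235, two-sided | r = .20, two-sided | r = .20, one-sided |
|---|---|---|---|---|
| 0% | 140 | .80 | .66 | .77 |
| 5% | 133 | .78 | .64 | .75 |
| 10% | 126 | .76 | .61 | .73 |
| 15% | 119 | .73 | .59 | .70 |
| 20% | 112 | .71 | .56 | .68 |

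Example, 126 analysed at r = .20, two-sided: 0.2027 × sqrt(123) − 1.960 = 0.288, and Phi(0.288) = .61.

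Sidedness matters little to the face-value column. Setting 80% at 140 one-sided gives .78, .76, .74 and .72.

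**Step 3: enrolment that would leave 140 analysable.** 140 / (1 − d), rounded up, is 148, 156, 165 and 175 for losses of 5%, 10%, 15% and 20%.

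**Step 4: if 150 were the enrolment.** The margin is 150 − 140 = 10, and 10 / 150 = 6.7%. A 10% loss would leave 135.

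**The case against.** The strongest reply is that losses should be few and their effect gradual. Much of this stands.

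- Claustrophobia, metal exposure and conditions that rule out exercise testing are exclusion criteria in Section 3.2. Section 5.0 describes metal screening as a check of eligibility. Failing it should mostly keep a person out of the study, so it is not counted here as a loss after enrolment.
- Additional heart rate needs only rest, stress and the first four exercise stages. Stopping later, in the progression to exhaustion, loses none of those data. Only stopping within the first four stages could.
- Section 5.0 calls claustrophobia in the scanner occasional. Section 3.4 pays participants on completing the imaging, which favours retention. Section 3.3 reviews recruitment every two months.
- Power does not collapse with one loss. On the face-value basis, 139 analysed gives .797 against .800.

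None of this supplies an allowance. The two-monthly review is directed at the number of participants recruited, not at usable two-visit data, and payment does not rescue an ended scan.

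A reader might also infer that strong reactors will leave the scanner selectively and so bias the results. The documents do not support that as a finding. They give no data on who drops out, the reason they state for ending a scan is claustrophobia, and the structural scan comes before the stress task. Under an assumed odds ratio of 3 per SD of the outcome (14% lost), r moves only from .20 to .19. Mean additional heart rate need not be affected by failed scans, because it is measured at Visit 1 and can be estimated from everyone with Visit 1 data.

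**Conclusion.** The concern holds in a limited form. The recruitment target equals the stated minimum, the analysis needs both visits, and nothing covers loss. The stated 80% is therefore not secured by recruiting 140. The 140 and 150 figures contradict each other and must be reconciled before the margin, if any, can be known.

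On the plan's own terms the cost is modest: about 2 points of power at 5% loss and about 9 to 10 at 20%. A reader might take 78% as the real power after 5% loss. It is not, because that figure rests on r = .235, which the plan does not state. At r of about .20, power is .66 two-sided or .77 one-sided before anyone is lost, so the larger part of the shortfall lies in how 140 was derived. Allowing for dropout on top of 140 would not by itself restore 80%.

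These figures assume one correlation test and loss unrelated to the outcome, at rates the documents do not give. They do not cover the training and testing of the machine-learning pattern.

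**What to change.** 1. Reconcile 140 in Sections 3.1 and 6.0 with 150 in Section 4.0.
2. State whether the number means participants enrolled or participants with usable Visit 1 and Visit 2 data.
3. Give an expected loss rate with its basis, and restate power at the expected analysable number, with the sidedness of the test. Recruitment need not rise if the lower power is stated openly. If 140 is meant as the analysable number, the enrolment figures in Step 3 apply.
4. State that mean additional heart rate will be estimated from everyone with Visit 1 data, whether or not the scan is usable.
5. Optionally, add one table comparing Visit 1 additional heart rate, sex and BMI between those with and without a usable scan. This uses data already collected.

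The cost is a few sentences and at most one table. No study procedure changes. The drawback is that the stated power becomes less favourable.
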